14.1.1 Incidence, incidence rates and number of events

The incidence of an adverse event is defined as the number of subjects with occurrence of this adverse event during the period of interest.

The incidence rate (crude incidence rate [CIR]) of an adverse event is defined as the number of subjects with occurrence of this adverse event during the period of interest divided by the total number of subjects N in the respective group (e.g., treatment group).

The incidence, incidence rate, the number of events, and the percentage of events will be summarized by PT (sorted by decreasing incidence rate in the MAR-CUTIS treatment group) for:

- TEAEs.
- Serious TEAEs.
- Non-serious TEAEs.
- TEAEs leading to withdrawal from the trial.

- ADEs.
- Serious ADEs.
- ADEs leading to withdrawal from the trial.
- Anticipated/Unanticipated ADEs.

Percentages will be calculated related to the total number of subjects/events presented in the respective table e.g., for the presentation of PTs for serious TEAEs percentages will be related to the number of subjects with serious TEAE/the total number of serious TEAEs, respectively.

For serious TEAEs, percentages will additionally be presented related to the total number of all subjects/events, respectively.

All tables above will be presented only for incidence rates greater than or equal to 2% in any treatment group.

The incidence, incidence rate, the number of events and the percentage of events will be summarized by SOC and PT (sorted alphabetically) for each:

- TEAEs.
- Serious TEAEs
 - Fatal TEAEs.
- Non-serious TEAEs.
- TEAEs leading to withdrawal from the trial
- ADEs
- Serious ADEs
 - Fatal ADEs.
- ADEs leading to withdrawal from the trial.
- Anticipated/Unanticipated ADEs.

Percentages will be calculated related to the total number of subjects/events presented in the respective table e.g., for the presentation of SOC and PT for serious TEAEs percentages will be related to the number of subjects with serious TEAE/the total number of serious TEAEs, respectively.

For serious TEAEs, percentages will additionally be presented related to the total number of all subjects/events, respectively.

If more than 10% subjects are withdrawn from the trial due to TEAE, the incidence and the incidence rate of TEAEs leading to withdrawal from the trial will be summarized by SOC and PT.

For all enrolled subjects, the incidence, incidence rate, the number of events and the percentage of events (related to the total number of events) will be summarized by SOC and PT (sorted alphabetically) for each:

- Pre-treatment non-TEAEs.
- Serious pre-treatment non-TEAEs.

Presentation will only be overall and not per treatment.

The number and percentage of events will be summarized by SOC and PT (sorted alphabetically) for the following TEAE / ADEs descriptors. Presentation will be for TEAEs / ADEs only:

- Intensity: mild, moderate, severe.
- Outcome: recovered, not yet recovered, recovered with sequelae, death, unknown.
- Action taken with the IMD: none, medication or therapy provided, IMD removed, concomitant medication changed, other.

Denominator for percentage calculation will be the number of all TEAEs / ADEs for presentation of overall SOCs, and the number of TEAEs/ADEs per SOC or PT respectively, for the presentation per SOC or PT, respectively.

Measures of location and variation will be calculated for:

- Duration of TEAEs.
- Time to onset of TEAEs.

The following listings will be produced for all enrolled subjects:

- Deaths.
- Serious adverse events other than death.
- Adverse events leading to withdrawal from the trial.

14.2 Laboratory assessments

A urine β -HCG pregnancy test will be performed at baseline (D0 visit) only. Results will be listed.

14.3 Wound infection

The analysis of wound infection described in Section [13.2.3](#) will be repeated for the SAF.

16 APPENDIX

16.1 Data derivation and analysis rules

The purpose of this section is to give technical details for the implementation of the SAP.

16.1.1 General specifications

16.1.1.1 Percentages and decimal places

If not otherwise specified, the following rules are applied:

- Percentages are presented to 1 decimal point.
- Percentages equal to 0 or 100 are presented as such without a decimal point.
- For descriptive summary statistics, the same number of decimal places as in the raw data are presented when reporting minimum and maximum values, 1 more decimal place when reporting mean, median, quartiles and confidence interval and standard deviation.
- P-values are presented to 3 decimal points. P-values <0.001 will be reported as such.
- Ratios are presented to 3 decimal points.

The above described displaying rules must not be changed (e.g., rounding) for the integrated clinical trial report text and are used 1:1 in the body report as well.

16.1.1.2 Presentation of descriptive statistics

Calculation of mean: if not otherwise specified, the arithmetic mean is used.

Table 2: Presentation of descriptive statistics in clinical trials

Number of non-missing values	n	Missing n	Mean	SD	Min	Q1	Median	Q3	Max	{CI for mean}
0	+	+	-	-	-	-	-	-	-	-
1.2.3.4	+	+	+	-	+	-	+	-	+	-
≥5	+	+	+	+	+	+	+	+	+	+

+ summary statistic will be presented; - summary statistic will not be presented.

CI = confidence interval, Max = maximum, Min = minimum, n = number of values, Q1 = first quartile, Q3 = third quartile, SD = standard deviation

For all ordinary levels of categorical parameters including missing values, both the number and the corresponding percentage is displayed. If no missing values occur at any time point/visit, then the number of missing values can be omitted.

16.1.1.3 Presentation of differences and changes

For differences between MAR-CUTIS and Dermabond, MAR-CUTIS will constitute the minuend and Dermabond the subtrahend.

16.1.1.4 Trial day count

The day of baseline visit is defined as trial Day 0.

Calculate the trial day according to the following rules:

- If date < trial Day 0, then trial day in SDTM = Date – trial Day 0.
- If date \geq trial Day 0, then trial day in SDTM = Date – trial Day 0 +1.

16.1.1.5 Presentation of units

If applicable, parameters will be displayed together with the used unit of measurement. The unit of measurement is enclosed in square brackets ([]).

16.1.1.6 Presentation of dates

Where applicable (e.g., in listings), dates will be displayed in ISO8601 format (example: 2014-09-29T12:16, see CDISC 2013). In case of incomplete dates, both the original value and the imputed value is displayed.

16.1.1.7 Handling of missing values

At each time point/visit, all subjects still in the trial (i.e., subjects who have not been withdrawn from the study) are reported. Missing values will be taken into account as missing in the analysis, unless specified differently (e.g., primary efficacy analysis). The number of observed values and the number of missing values must add up to the number of subjects in the trial at the respective time point/visit.

Unless otherwise specified in the SAP, missing values will not be imputed (with the sole exception of primary efficacy data, as discussed in Section 13.1.1). If missing values are imputed, the result of all imputation strategies and newly derived information must be stored in the ADaM data set.

Imputed values will be listed in the subject data listing and marked as imputed.

16.1.1.8 Visit windows

Recorded data will be analyzed in accordance to the respective visit and the Schedule of Assessments. Time window violations will not be considered.

If an assessment is scheduled at the ED visit, the ED visit will be analyzed together with the last assessment before ED (Month 1 or Month 3) to provide an estimate of the “last assessment”.

16.1.1.9 Conversion of time intervals

If a time interval was calculated in minutes, hours or days and needs to be converted into months or years, the following conversion factors will be used:

- 1 month = 30 days.
- 1 year = 365.25 days.

16.1.1.10 Mandatory tables without data

Recommended tables must be created. If no subject qualifies for the table, the header will be created and the table itself will be replaced by “No subject in this category”.

16.1.1.11 Unscheduled visits

Unscheduled visits are time points not planned in the protocol.

In listings, unscheduled visits will be listed as recorded. All visits will be ordered chronologically including the dates of unscheduled visits.

Unscheduled visits will be excluded from the per time point/visit presentation.

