
 
To compare the wound infection incidence between both treatment groups.
 
	
 
Wound infection incidence assessed at the Day 10, Month 1, and Month 3 visits or at the Early Discontinuation visit (diagnosed according to the Centers for Disease Control and Prevention [CDC] criteria for surgical site infection [Section 15.1]).
 
Wound infection assessed on a binary scale (“1 - yes” or “0 - no”) for the following criteria: 
 
Presence of erythema
 
Presence of edema
 
Presence of pain at rest
 
Presence of elevated temperature
 
 A total score will be calculated for each subject.
 

 
To evaluate the investigator satisfaction with the cosmetic outcome after the closure of the target surgical incision/laceration with MAR-CUTIS versus Dermabond Advanced.
 
	
 
Investigator-completed POSAS done at the Month 1 and Month 3 visits or at the Early Discontinuation visit (if Early Discontinuation occurs before Month 1).
 

	

Investigator-completed Modified Hollander Cosmesis Scale (mHCS) done at the Day 10 and Month 1 visits or at the Early Discontinuation visit (if Early Discontinuation occurs before Month 1).

To evaluate the subject comfort with the device during and after treatment with MAR-CUTIS versus Dermabond Advanced.

	

A questionnaire related to subject experience and satisfaction with the device completed by the subject at the Day 10 and Month 1 visits or at the Early Discontinuation visit (if Early Discontinuation occurs before Month 1).

A subject-related questionnaire completed by the investigator at the Day 0 and Month 1 visits or at the Early Discontinuation visit (if Early Discontinuation occurs before Month 1).

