### 9.3.6 Other Safety Assessments

Wound infection incidence, diagnosed according to the CDC criteria for surgical site infection, will be assessed by an investigator at the Day 10, Month 1, Month 3/Early Discontinuation, and any unscheduled study visits. In addition, the infection will be assessed on a binary scale (“1 - yes” or “0 - no”) for the criteria below. A total score will be generated for each subject.

- Presence of erythema
- Presence of edema
- Presence of pain at rest
- Presence of elevated temperature

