13.2.3 Wound infection

Wound infection evaluation, diagnosed according to the CDC criteria for surgical site infection, will be assessed by a treating physician and recorded in the e-CRF.

13.2.3.1 Wound infection incidence at Day 10, Month 1 and Month 3

Wound infection incidence, evaluated through the presence of erythema, edema, pain at rest or elevated temperature, will be summarized with descriptive statistics at the Day 10, Month 1, and Month 3 study visits.

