13.2.3.2 Wound infection evaluated with a binary scale

Wound infection will be additionally assessed at the same timepoints by calculating a Wound Infection Score utilizing a binary scale as follows:

$$\text{Wound Infection Score} = I_{\text{erythema}} + I_{\text{edema}} + I_{\text{pain_rest}} + I_{\text{elevated_temperature}},$$

where the four indicator variables above are equal to 1 if the wound reported the presence of erythema, edema, pain at rest or elevated temperature, and equal to 0 if the presence of each category is not recorded or is missing. Thus, the Wound Infection Score will have a maximum value of 4, and a minimum value of 0.

Descriptive statistics of the Wound Infection Score will be presented by visit.

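### Wound infections seen only at unscheduled visits are left out of every planned wound-infection summary, so reported infection incidence can be understated

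*SAP*

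**What the plan says.** Protocol Section 6 sets the secondary objective: "To compare the wound infection incidence between both treatment groups". The matching endpoint is "Wound infection incidence assessed at the Day 10, Month 1, and Month 3 visits or at the Early Discontinuation visit", and Protocol Section 9.3 lists the same occasions. Neither names unscheduled visits.

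Protocol Section 9.3.6 goes further. It has infection "assessed by an investigator at the Day 10, Month 1, Month 3/Early Discontinuation, and any unscheduled study visits", and applies the four-sign score (erythema, edema, pain at rest, elevated temperature) to the infection as well.

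SAP Section 13.2.3.1 says that incidence "will be summarized with descriptive statistics at the Day 10, Month 1, and Month 3 study visits". For the score, SAP Section 13.2.3.2 says: "Descriptive statistics of the Wound Infection Score will be presented by visit". SAP Section 14.3 repeats these analyses on the Safety Set. SAP Sections 13.3 and 16.1.1.8 bring in the early discontinuation visit.

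SAP Section 16.1.1.11 then sets the general rule: "Unscheduled visits will be excluded from the per time point/visit presentation". The same section keeps the data elsewhere: "In listings, unscheduled visits will be listed as recorded".

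**The concern.** Infection can come and go between planned visits. The plan asks investigators to assess it whenever a subject comes in, then tabulates only what was found on planned occasions. No table counts subjects who were infected at any time up to a given point, which is the quantity that an incidence objective calls for.

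The SAP treats dehiscence differently. Sections 13.1 and 13.2.1 bring unscheduled visits into the Day 10 and Month 1 rates, and a dehiscence once seen stays counted even if a later visit shows none. Infection has no such exception, so the general rule applies to it.

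At stake is the accuracy of a secondary endpoint that is also reported as a safety result. Few infections are likely, so each omitted case is visible in the percentages.

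**Working it through.** **1. Where each document counts an infection**

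| Occasion | Assessed (Protocol 9.3.6) | Endpoint wording (Protocol 6 and 9.3) | Infection summaries (SAP 13.2.3, 14.3, 13.3) |
|---|---|---|---|
| Day 10, Month 1, Month 3 | yes | yes | yes |
| Early discontinuation | yes | yes | yes, through 13.3 |
| Unscheduled visit | yes | not named | no (16.1.1.11); listings only |

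The last row is the gap. Nothing elsewhere in the SAP fills it for infection.

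**2. When a case drops out**

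Two conditions must both hold: the infection is seen at an unscheduled visit, and no later planned or early discontinuation visit records it. There is room for this. Taking a month as 30 days (SAP Section 16.1.1.9), Day 10 to Month 1 is about 20 days and Month 1 to Month 3 about 60 days. SAP Section 13.2.3.1 evaluates infection through the signs present, and Section 13.2.3.2 scores a sign as 0 when it is not recorded or is missing. A subject who has recovered by the next planned visit could thus score 0 throughout.

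**3. Direction**

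Leaving visits out can lower the number of subjects ever infected or leave it unchanged. It cannot raise it.

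**4. Size, as an illustration**

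The plan gives no expected infection figure for either arm, so there is none to reproduce. Inputs:

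- *r* = 3.6%, the infection rate that Protocol Section 5 gives for other skin adhesives. It is not a trial assumption.
- 126 MAR-CUTIS and 63 Dermabond Advanced subjects (Protocol Section 10.2).
- *u* = share of infected subjects seen only at unscheduled visits. The documents give no value; 0% to 50% is assumed here.

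Expected infected subjects: 126 × 0.036 = 4.5 and 63 × 0.036 = 2.3; in total 189 × 0.036 = 6.8.

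Reported incidence = *r* × (1 − *u*); subjects lost = 6.8 × *u*.

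| *u* (assumed) | Reported incidence | Subjects lost of 189 |
|---|---|---|
| 0% | 3.60% | 0 |
| 10% | 3.24% | 0.7 |
| 20% | 2.88% | 1.4 |
| 30% | 2.52% | 2.0 |
| 50% | 1.80% | 3.4 |

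One omitted subject changes the arm's incidence by 1/126 = 0.8 percentage points for MAR-CUTIS and 1/63 = 1.6 points for Dermabond Advanced.

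**The case against.** Four arguments count against the point.

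- **Adverse events.** Protocol Section 9.3.2.1 has every adverse event recorded from consent to the last visit, and SAP Section 14.1.1 tabulates treatment-emergent events by arm. The 2% display threshold applies to the preferred-term tables; the tables by system organ class and preferred term that follow carry none. A reader might infer that an infection treated between visits disappears from the report. The documents do not support that: it stays in the listings and should appear in these tables. But those tables count MedDRA terms. They give neither CDC-criteria incidence nor the four-sign score, so they do not answer the secondary objective, and no step is planned to reconcile the two counts.
- **Look-back.** Protocol Sections 8.2.2 to 8.2.4 make the infection evaluation at planned and early discontinuation visits conditional on an infection having occurred. That can be read as covering the time since the last visit, in which case nothing may be lost. This stands as a possibility. No look-back period is stated, however, and the SAP's wording points to signs present at the visit.
- **Endpoint wording.** The by-visit tables match the endpoint as Protocol Sections 6 and 9.3 word it. That is so, and it shows that those sections and Section 9.3.6 need to be reconciled.
- **Limited role.** The endpoint is descriptive, no safety comparison is tested, and the rule is the same for both arms. All of this stands. It limits the consequence but does not make the count complete.

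**Conclusion.** The point holds in a conditional form: wound infection incidence can be understated in the planned infection summaries. It is understated only if some infections are seen at unscheduled visits and not recorded at a later planned or early discontinuation visit.

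The documents do not fix the size. At an illustrative 3.6% rate, with 0% to 50% of infected subjects seen only at unscheduled visits (an assumption), reported incidence lies between 3.6% and 1.8%, and 0 to about 3.4 of 189 subjects are lost.

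Two stronger readings are tempting. One is that incidence will certainly be too low because infected subjects usually come in between visits; the documents say nothing about how often that happens. The other is that the rule favours one product; it is identical in both arms, and nothing in the documents suggests that the omitted share differs between them. The dehiscence endpoint, its noninferiority test and its power are not affected.

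**What to change.** Add to SAP Section 13.2.3 a per-subject cumulative summary of any wound infection, by arm, up to Day 10, Month 1 and Month 3. For example: *a subject counts as infected up to a visit if a wound infection was diagnosed at any planned, unscheduled or early discontinuation visit after application and up to that visit, whether or not it was still present later.* State that Section 16.1.1.11 does not apply to this summary. Use all subjects of the arm in the analysis set as denominator, because the default in SAP Section 8.1 is subjects still in the trial. Produce it for the FAS and, through Section 14.3, for the Safety Set. Keep the by-visit tables as a supplement.

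Align Protocol Sections 6, 9.3 and 9.3.6 with SAP Sections 13.2.3.1 and 16.1.1.11 on which visits count, and state whether the infection item at a planned visit covers the time since the previous one.

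The cost is one SAP sentence and one table. Protocol Section 9.3.6 already requires the assessments, so no new data are needed, and the handling of dehiscence in SAP Sections 13.1 and 13.2.1 is a ready model for unscheduled visits.

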16.1.2 Disposition

16.1.2.1 Subject withdrawal

Reasons for subject withdrawal as specified in the End-of-trial page of the e-CRF will be used.

16.1.2.2 Protocol deviations

Protocol deviations are based on the analysis dataset ADDV. Major protocol deviations are retrieved from the respective SDTM dataset (SDTM.DV.DVCAT). No further protocol deviations are programmed in the analysis datasets for ADDV (if not otherwise specified in the SAP).

16.1.3 Demographics and other baseline characteristics

16.1.3.1 Subject demographics

Derivation of age

Age as derived in SDTM.DM.AGE will be used.

Derivation of BMI:

BMI is extracted from the SDTM.

Derivation of race:

If for race more than 1 entry per subject is documented, a category “multiple” will be created.

16.1.3.2 Prior and concomitant medication

Prior and concomitant medication is collected as of enrollment in the e-CRF and described like that in the trial protocol. For the analysis, the definition as described in the following is used.

The following rules are used to define the categories “prior” and “concomitant” medication.

Pre-requisite is a complete date of application of IMD.

Stop of medication	Condition	Category
Date		
Complete date is available	Stop date is earlier than date of the start of the application of IMD.	Prior
Missing month	Year of stop date is earlier than year of the start of the application of IMD.	Prior
Missing day	Month/year of stop date are earlier than month/year of the start of the application of IMD.	Prior
Otherwise		Concomitant

Medication ticked in the e-CRF as “ongoing” will be classified as concomitant.

16.1.4 Safety analysis

16.1.4.1 Adverse events

[figure not shown]
The result of all imputation strategies (e.g., incomplete start dates of adverse events and new derived information (e.g., treatment-emergent flag) must be stored in ADaM data set.

Handling of missing date information

The term missing date refers to a completely missing date or to an incomplete date where parts are not available.

The following imputation strategy is applied.

Missing start and end date will be imputed conservatively, i.e., missing values will be imputed in such a way that the duration of the adverse event is considered with the longest possible duration and such that, whenever the adverse event may potentially start after first IMD application, the adverse event will be handled as a TEAE.

I1-I4: imputation steps

C1-C4: checkpoints

AE = adverse event, IMP = investigational medicinal product

Figure 2: Graphical overview about the imputation strategy

Further explanations on the flow chart:

The different steps of the displayed imputation strategy must be completed from the first to the last step. All procedures in each step must be completed in the order given.

- Imputation:
 - I1: Impute with date of the start of the application of IMD
 - I2:
 - a) Impute with first calendar day and/or first calendar month
 Imputation will be done based on the available partial information starting with month and then day. The respective first month and day will be chosen for imputation:

Missing date	Imputed date
2014-Mar	2014-Mar-01
2014	2014-Jan-01

- I3: Impute with date of informed consent signed
- I4:
 - a) Impute with last calendar day and/or calendar last month
 Imputation will be done based on the available partial information starting with month and then day. The respective last month and day will be chosen for imputation:

Missing date	Imputed data
2014-Mar	2014-Mar-31
2014	2014-Dec-31

For February leap years must to be taken into account when calculating the last day in February.

1.1.

- Checkpoints
 - C1: The decision must be taken based on the available information (date) before imputation.
 - C2: Adverse event stop date before the start of the application of IMD

1.2. 1) The decision must be taken based on the available information (date) before imputation.

2) If the end date is completely missing (with or without the information that the adverse event was continuing), this will be considered as after the start of the application of IMD.

- C3: The decision must be taken based on the available information (date) before imputation.
- C4: The decision must be taken based on the available information (date) before imputation.

A replacement of missing year for adverse event start information is not foreseen. If needed, this will be considered on a case-by-case decision which must be documented together with the documentation of ADaM data sets.

Assessment of TEAEs

The assessment whether an adverse event is a TEAE will be done after replacement of missing date information.

Assignment adverse events to time periods

Assignment of adverse events to time periods will be done after replacement of missing date information.

List of deaths

Death will be identified by outcome of adverse event equals “Death”.

Time to onset of adverse events

Time to onset of adverse events will be calculated based on the start of the application of IMD based on the imputed value for adverse event start date.

Subject experiencing a non-serious treatment emergent adverse event

All subjects who had at least 1 non-serious TEAE will be taken into account regardless of the experience of a serious TEAE.

